6.2.3 End of trial and follow-up period

6.2.3.1 End of treatment

All patients will remain on study treatment until the last patient entered has completed at least six months of treatment. Based on the number of OEs, the operations committee will declare the end of the trial date and ask that all patients be brought in for their end of trial visit within a certain time period, which will be communicated by the trial team.

The EOT visit should take place for all patients when they discontinue study drug.

Patients who discontinue the study medication early should be registered as “withdrawn” and patients who complete the full treatment period should be registered as completed in the IRT.

After termination of study drug the patient should be switched to an appropriate non study anticoagulant and antiplatelet regimen (if required) according to the local practices. See [Appendix 10.2](#).

Assessments should be performed as mentioned in the [Flow Chart](#).

6.2.3.2 Follow up visit

All patients should have a follow-up visit performed four weeks after EOT. During this visit, concomitant medications, AEs, SAEs and OEs (including signs and symptoms of bleeding) during the 4 week period after last dose of study drug will be collected.

Patients who discontinue the study medication early should return to their original visit schedule after this follow up visit (see [Section 6.2.2](#)).

6.2.3.3 Final Visit

The final visit will be conducted in all patients who discontinue study treatment early at the time the trial conclusion is declared. Assessments will be done according to the flowchart.

6.2.3.4 Vital Status and Outcome Event Collection

It is important to record the vital status and OEs of all randomised patients at the end of the trial.

If a site has difficulty contacting a patient at the end of the trial, site staff should make a minimum of three documented attempts to contact the patient using different methods (i.e. phone, email, certified letter, other). In the absence of reaching the patient directly, alternative approaches which are allowable via local regulations and IRB/IEC should be used to establish vital status (at minimum) and incidence of thrombotic events and major bleeds (where possible).

Proprietary confidential information.

© 2016 Boehringer Ingelheim International GmbH or one or more of its affiliated companies. All rights reserved.

This document may not - in full or in part - be passed on, reproduced, published or otherwise used without prior written permission.

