5.2 SAFETY

5.2.1 Endpoints of safety

The primary endpoint for this trial is time to first ISTH MBE or CRNMBE. For definition of CRNMBE see [section 5.2.2.1](#).

Proprietary confidential information.

© 2016 Boehringer Ingelheim International GmbH or one or more of its affiliated companies. All rights reserved.

This document may not - in full or in part - be passed on, reproduced, published or otherwise used without prior written permission.

Other safety endpoints are:

1. Major bleeding (ISTH)
2. CRNMBE (for definition see [section 5.2.2.1](#))
3. Clinically relevant bleeding measured using the following definitions:
 - Bleeding Academic Research Consortium (BARC) ≥ 3
 - TIMI group - Major and Minor
4. Minor and total bleeding (ISTH, BARC and TIMI)
5. Intracranial haemorrhage

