5.2.2 Assessment of adverse events

5.2.2.1 Assessment of Bleeding events

Patients should be carefully assessed for signs and symptoms of bleeding. Bleeding will be classified as major, Clinically Relevant Non Major Bleeding Event (CRNMBE) or minor. Major bleeds will be further sub classified as life-threatening and other major bleeds. The location of the bleeding including the specific critical area or organ into which the bleeding occurred and whether or not it prolongs hospitalisation will be recorded. The following definitions are specified for bleeds:

Definition of a major bleed

Major bleeds will be defined according to the ISTH definition of a major bleed, as follows [[R05-0344](#)].

- Symptomatic bleeding in a critical area or organ, such as intracranial, intraspinal, intraocular, retroperitoneal, intra-articular or pericardial, or intramuscular with compartment syndrome

and/or

- Bleeding associated with a reduction in haemoglobin of at least 2g/dL (1.24mmol/L), or leading to transfusion of two or more units of blood or packed cells¹

and/or

- Fatal bleed

Definition of a CRNMBE

A clinically relevant non-major bleeding event is a clinically overt bleed that does not meet

¹ Bleeding should be overt and the haemoglobin drop should be considered to be due to and temporally related to the bleeding event.

the criteria for a major bleed but prompts a clinical response, in that it leads to at least one of the following:

- A hospital admission for bleeding
- or
- A physician guided medical or surgical treatment for bleeding
- or
- A physician guided change, interruption¹ or discontinuation of study drug.

Definition of a minor bleed

Minor bleeds are clinical bleeds that do not fulfil the criteria for major bleeds. Minor bleeds will be further divided to those that are CRNMBE, (see above) and those that are not.

Definition of a life-threatening bleed

Major bleeds are to be classified as life-threatening if they meet one or more of the following criteria:

- Fatal, or symptomatic intracranial bleed; reduction in haemoglobin of at least 5g/dL; transfusion of at least four units of blood or packed cells, associated with hypotension requiring the use of i.v. inotropic agents; necessitated surgical intervention.

Definition of intracranial haemorrhage (ICH)

Intracranial haemorrhage (ICH) comprises the subtypes of intracerebral bleeds, subdural bleeds, epidural bleeds and subarachnoid bleeds and will be recorded.

Definition of a fatal bleeding

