7.2 NULL AND ALTERNATIVE HYPOTHESES

Two safety hypotheses (110mg Dabigatran Etexilate (DE-DAT) vs. warfarin-TAT and 150mg DE-DAT vs. warfarin-TAT) will be tested:

1. 110mg DE-DAT is non-inferior to warfarin-TAT with respect to MBE/CRNMBE over the duration of the trial
2. 150mg DE-DAT is non-inferior to warfarin-TAT with respect to MBE/CRNMBE over the duration of the trial.

To control the Type I error rate at a one-sided 0.025 level, a hierarchical procedure for multiple testing will be used to test the above hypotheses. Additional testing for safety and efficacy endpoints will also be included in this hierarchical procedure. The following hierarchical procedure will be applied:

Step 1 – Non-inferiority of 110mg DE-DAT to warfarin-TAT in MBE/CRNMBE is met at the one-sided 0.025 level of significance

Step 2 – Non-inferiority of 150mg DE-DAT to warfarin-TAT in MBE/CRNMBE is met at the one-sided 0.025 level of significance

Step 3 – Non inferiority of 150mg DE-DAT and 110mg DE-DAT combined to warfarin-TAT in DTE and unplanned revascularisation by PCI/CABG is met at the one-sided 0.025 level of significance

Proprietary confidential information.

© 2016 Boehringer Ingelheim International GmbH or one or more of its affiliated companies. All rights reserved.

This document may not - in full or in part - be passed on, reproduced, published or otherwise used without prior written permission.

Step 4 – Superiority of 110mg DE-DAT to warfarin-TAT in MBE/CRNMBE is met at the one-sided 0.025 level of significance

Step 5 – Non inferiority of 150mg DE-DAT and 110mg DE-DAT combined to warfarin-TAT in DTE is met at the one-sided 0.025 level of significance

Step 6 – Superiority of 150mg DE-DAT to warfarin-TAT in MBE/CRNMBE is met at the one-sided 0.025 level of significance

If any of the steps above fail to meet statistical significance, the testing procedure will stop at that step and subsequent tests will not be performed.

The Non-Inferiority (NI) margin used for MBE/CRNMBE will be 1.38 (on the relative HR scale). See [Section 7.6](#) for a clinical justification of this margin. The upper bound of the Wald confidence interval (CI) of the HR of DE-DAT vs. warfarin-TAT (one-sided 97.5%) will be compared to this NI margin for the NI testing.

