Description of change	
The dual primary endpoints for this trial are a composite endpoint of efficacy and a safety endpoint:
 
 1. Time to death or first thrombotic event (DTE) (all death, MI, stroke/SE) 2. Time to first ISTH Major Bleeding Event (MBE) 
The secondary endpoints of efficacy are (all time to event endpoints):
 
 1. Individual outcome events: 
 ○ All death 
 ▪ Cardiovascular death ▪ Non-cardiovascular death ▪ Undetermined ○ MI ○ Stroke ○ SE ○ Stent thrombosis 2. Composite endpoint of death + MI + stroke 3. Repeated revascularisation by PCI/CABG 
Has been changed to:
 
The primary endpoint for this trial is a safety endpoint. See section 5.2.1. There are no primary efficacy endpoints.
 
The secondary efficacy endpoints (all time to first

Proprietary confidential information.

© 2016 Boehringer Ingelheim International GmbH or one or more of its affiliated companies. All rights reserved.

This document may not - in full or in part - be passed on, reproduced, published or otherwise used without prior written permission.

Number of global amendment	2
	
event) are:
 
 1. A combined endpoint of thrombotic events or death (DTE: all death + MI + stroke/SE) and unplanned revascularisation by PCI/CABG 2. A combined endpoint of thrombotic events or death (DTE: all death + MI + stroke/SE) 3. Individual outcome events: 
 ○ All death 
 ○ Cardiovascular death ○ Non-cardiovascular death ○ Undetermined ○ MI ○ Stroke ○ SE ○ Stent thrombosis 4. Composite endpoint of death + MI + stroke 5. Unplanned revascularisation by PCI/CABG
Rationale for change	Efficacy parameters including combined endpoints (e.g. all death, myocardial infarction, stroke/systemic embolism) will now be evaluated as secondary endpoints.
Section to be changed	5.1.2.6 Repeated revascularisation by PCI/CABG

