6.6 HANDLING OF MISSING DATA AND OUTLIERS

A major goal of the trial is to obtain virtually complete follow-up of vital status and full collection of outcome event data. As mentioned in [Section 7.4](#), all patients lost to follow-up will be treated as censored at the time of last known vital status. This section contains details of how censoring will be performed for patients who do not experience outcome events.

The CTR will contain a summary of the number and percentage of patients with (and without) complete follow-up of vital status in each treatment group.

Due to the nature of the adjudication process, it may not be possible to classify bleeds under every bleed definition (i.e. TIMI and BARC). In these instances, the bleed classification will be left missing and no imputation will be attempted. Classification of bleeds under the ISTH definitions should not be left missing by the IAC.

In general, missing investigator INR ranges will be imputed with the standard guideline range for this patient population which is 2-3. The exception to this is for patients in Japan who are ≥ 70 years old. The guideline range for these patients is 2 – 2.6.

Missing or incomplete AE dates/times are imputed according to BI standards (see “Handling of missing and incomplete AE dates”) [[1](#)]. The same philosophy will be applied to missing or incomplete outcome event and concomitant medication dates/times. Incomplete dates of temporary study medication discontinuation and restart will be imputed. See the TSAP Analysis Dataset (ADS) Plan for further details. Other special handling for missing/incomplete dates/times will be documented in the RPM.

Other missing data will not be imputed. If date of birth/age is missing for a patient, they will not be included in models that use age group as a stratifying factor.

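### The fallback instruction for tracing unreachable patients names thrombotic events and major bleeds but omits CRNMBE and unplanned revascularisation, both components of tested endpoints

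*Protocol*

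**What the plan says.** Protocol 6.2.3.4 contains a general aim and a specific instruction. The aim is: "It is important to record the vital status and OEs of all randomised patients at the end of the trial". The instruction applies when a patient cannot be reached directly at the end of the trial, for which at least three documented attempts are required. Sites are then to use other permitted routes to "establish vital status (at minimum) and incidence of thrombotic events and major bleeds (where possible".

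The endpoints are broader than that instruction:

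- Protocol 5.2.1: "The primary endpoint for this trial is time to first ISTH MBE or CRNMBE".
- Protocol 5.2.2.1: "A clinically relevant non-major bleeding event is a clinically overt bleed that does not meet" the major-bleed criteria. CRNMBE is therefore outside the term used in the tracing instruction.
- Protocol 7.2, Step 3, the first efficacy test: "Non inferiority of 150mg DE-DAT and 110mg DE-DAT combined to warfarin-TAT in DTE and unplanned revascularisation by PCI/CABG".

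The outcome-event list in Protocol 5.2.2.2 includes any bleed but does not include revascularisation. SAP 6.6 sets the ambition: "A major goal of the trial is to obtain virtually complete follow-up of vital status and full collection of outcome event data".

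On time at risk, Protocol 7.3.1 and SAP 6.6 censor patients lost to follow-up at their last known vital status. SAP 7.4 includes a vital-status date obtained from a third party among the dates that determine when a patient was last seen.

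**The concern.** A site that follows the tracing sentence to the letter would ask a hospital or treating physician whether the patient is alive and has had a thrombotic event or a major bleed. It would not be prompted to ask about an admission or treatment for a lesser bleed, or about a repeat PCI or CABG.

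This matters because of the censoring rule. If a traced patient were censored at the last full contact, unsought CRNMBE would create no false event-free time. Under the plan, the patient can stay in the risk set up to the date on which someone else confirmed vital status. Over that interval one component of the primary endpoint was looked for and the other was not. The same applies to revascularisation in Step 3, except where it comes to light through a traced MI or stent thrombosis.

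**Working it through.** **1. Text, side by side**

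| Component | Tested in | Covered by the opening aim of 6.2.3.4 | Named in the tracing instruction |
|---|---|---|---|
| Death, MI, stroke/SE | Steps 3 and 5 | yes | yes (vital status, thrombotic events) |
| ISTH major bleed | Steps 1, 2, 4, 6 | yes (any bleed) | yes |
| CRNMBE | Steps 1, 2, 4, 6 | yes (any bleed) | no |
| Unplanned revascularisation | Step 3 | no (not an outcome event in 5.2.2.2) | no |

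**2. The plan's own figures (Protocol 7.6)**

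Inputs: one-sided alpha 0.025, margin 1.38, 334 events per pair of arms, 14% with an event at one year, uniform accrual over 24 months, follow-up of 6 to 30 months. A true HR of 1 is assumed; the plan does not state it.

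- Power = Φ(√334 / 2 × ln 1.38 − 1.96) = Φ(0.983) = 83.7%, against 83.6% stated.
- Hazard λ = −ln(1 − 0.14) = 0.151 per year.
- Event probability = 1 − (e^(−0.5λ) − e^(−2.5λ)) / (2λ) = 0.1994. This gives 834 × 0.1994 = 166 events per arm (167 stated) and 2502 × 0.1994 = 499 in total (about 500 stated).

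The design figures reproduce.

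**3. Events not sought**

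The documents give no tracing rate, untraced interval or CRNMBE share. Assumed ranges: 2–5% of patients traced only indirectly, 0.5–1.0 year untraced each, CRNMBE 50–75% of first primary events.

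- Low: 2502 × 0.02 × 0.5 × 0.151 × 0.50 = 1.9
- High: 2502 × 0.05 × 1.0 × 0.151 × 0.75 = 14.2

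That is about 2 to 14 of 500, or 0.4% to 2.8%.

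For wider limits, let u be the share traced only indirectly (1–10%), s the CRNMBE share (40–80%), and f the fraction of those patients' events that fall in the untraced interval (0.5–1). Events missed = 500 × u × s × f, from 500 × 0.01 × 0.4 × 0.5 = 1 to 500 × 0.10 × 0.8 × 1 = 40. At the extreme, 334 × (1 − 0.08) = 307 events per pair remain, and power at a fixed analysis time is 80.6%.

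**4. Effect on the hazard ratio**

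*Equal tracing, same treatment effect on both components.* Both arms lose the same fraction of events, so the ratio is essentially unchanged.

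*Tracing differs by arm.* The observed HR is multiplied by (1 − u_DE·s·f) / (1 − u_W·s·f).

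| Traced, DE vs warfarin | Multiplier |
|---|---|
| 5% vs 2% | 0.976 to 0.994 |
| 2% vs 5% | 1.006 to 1.025 |
| 10% vs 2% | 0.935 to 0.984 |
| 2% vs 10% | 1.016 to 1.070 |

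For example, with s = 0.8 and f = 1, 5% vs 2% gives 0.960 / 0.984 = 0.976.

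*Treatment effect differs by component.* The composite HR is roughly an average of the CRNMBE and major-bleed HRs, with CRNMBE weighted s. Equal loss changes that weight to s(1 − uf) / (1 − s·uf). With uf = 0.10 and s = 0.6 this is 0.54 / 0.94 = 0.574, a shift of 0.026. The composite moves slightly towards the major-bleed HR, and the direction depends on which component has the larger effect.

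**The case against.** The best defence is that the section does ask for more. Its opening sentence covers every outcome event in every randomised patient, and any bleed is an outcome event. The tracing sentence is a last resort with tiered wording, and naming the hard events that indirect sources are most likely to hold is a reasonable priority. Most ascertainment happens earlier: a bleeding questionnaire at each visit, entry of outcome events within 24 hours of awareness, and attempts about every three months to locate lost patients. Only the interval after last contact is exposed. An event-driven trial can also run longer to recover events.

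Much of this stands, and it rules out three stronger readings that a reader might infer.

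- *CRNMBE is not collected in these patients.* The text does not say so. The aim covers CRNMBE and the operative sentence is narrower, so the two disagree. The aim does not cover revascularisation, however, because that is missing from the outcome-event list.
- *Under-ascertainment pulls the comparison towards no difference and so favours non-inferiority.* Equal loss leaves the ratio about where it was. Unequal loss can push it either way, and the documents give no basis for a direction.
- *The sentence is demonstrably left over from before Amendment 2.* Its items match the superseded co-primaries, "Time to death or first thrombotic event (DTE) (all death, MI, stroke/SE" and "Time to first ISTH Major Bleeding Event (MBE", and the amendment log records no change to 6.2.3.4. That is suggestive only. Repeated revascularisation was already a secondary endpoint then, so on that reading the sentence never listed every endpoint.

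The defence does not remove the mismatch between the instruction that sites would act on and the endpoint whose time at risk runs to a vital-status date. Qualifying the effort by what is possible does not add an item to the list.

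**Conclusion.** The point holds as an internal mismatch of limited size. For patients who cannot be reached, the operative sentence does not name one component of the primary endpoint and one of Step 3, while the censoring rules can credit those patients with event-free time for both.

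The 2 to 14 events rest wholly on the assumed tracing rate, untraced time and CRNMBE share. They are events not sought; fewer would be recovered, since other sources may not hold them all. The loss of precision is slight at plausible tracing rates. Bias needs tracing that differs by arm, which is possible in an open-label trial but not shown, or different effects on CRNMBE and major bleeds. Nothing here shows that a test conclusion would change. The case for acting is that the gap touches the primary endpoint and is cheap to close.

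**What to change.** Amend the tracing sentence in Protocol 6.2.3.4 so that, beyond vital status, sites seek where possible the occurrence and date of all bleeding outcome events including CRNMBE, and of unplanned revascularisation, as well as thrombotic events. Adding revascularisation to the outcome-event list in 5.2.2.2 would bring the section's opening aim into line. Add one eCRF field for the date up to which bleeding status is known, so that time at risk for the primary endpoint can be checked against it.

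The cost is slightly more record review and one eCRF field. Indirect sources will not hold every CRNMBE, particularly one that consisted only of a change to study drug, so ascertainment will improve without becoming complete.

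If close-out contacts are already finished (SAP 7.4 places final visits for patients who stopped treatment early between February and April 2017), the wording can no longer help. The remaining option is a sensitivity analysis that censors indirectly traced patients at the last date on which all components of the primary endpoint were assessed.

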6.2.3.5 Withdrawal of consent

Patients that discontinue medication and express desire to reduce their degree of participation should be presented with a reduced follow-up option as described in [Section 6.2.2](#).

If the patient is not willing to continue in the trial and withdraws consent refer to [Section 3.3.4.1](#).

Proprietary confidential information.

© 2016 Boehringer Ingelheim International GmbH or one or more of its affiliated companies. All rights reserved.

This document may not - in full or in part - be passed on, reproduced, published or otherwise used without prior written permission.

7. STATISTICAL METHODS AND DETERMINATION OF SAMPLE SIZE

7.1 STATISTICAL DESIGN - MODEL

This is a prospective, randomised, open label, blinded endpoint (PROBE), active comparator trial and the clinical endpoints are being adjudicated by an IAC in a blinded fashion. The study will employ a time to first event analysis (using a stratified Cox proportional hazards regression model) and it is assumed that all patients will remain on study treatment until the last patient entered has completed at least six months of treatment (up to an anticipated maximum duration of approximately 30 months for the first patient entered). The trial will be monitored by an independent DMC.

This study is designed to test a safety hypothesis in NVAf patients that have undergone a successful PCI (elective or due to ACS) with stenting and were treatment naïve or were receiving oral anticoagulant treatment (either with warfarin, another VKA or other novel oral anticoagulant) before the procedure.

The primary outcome is stated in [Section 5.2.1](#).

1. ISTH MBE and CRNMBE

7.2 NULL AND ALTERNATIVE HYPOTHESES

Two safety hypotheses (110mg Dabigatran Etexilate (DE-DAT) vs. warfarin-TAT and 150mg DE-DAT vs. warfarin-TAT) will be tested:

1. 110mg DE-DAT is non-inferior to warfarin-TAT with respect to MBE/CRNMBE over the duration of the trial
2. 150mg DE-DAT is non-inferior to warfarin-TAT with respect to MBE/CRNMBE over the duration of the trial.

To control the Type I error rate at a one-sided 0.025 level, a hierarchical procedure for multiple testing will be used to test the above hypotheses. Additional testing for safety and efficacy endpoints will also be included in this hierarchical procedure. The following hierarchical procedure will be applied:

Step 1 – Non-inferiority of 110mg DE-DAT to warfarin-TAT in MBE/CRNMBE is met at the one-sided 0.025 level of significance

Step 2 – Non-inferiority of 150mg DE-DAT to warfarin-TAT in MBE/CRNMBE is met at the one-sided 0.025 level of significance

Step 3 – Non inferiority of 150mg DE-DAT and 110mg DE-DAT combined to warfarin-TAT in DTE and unplanned revascularisation by PCI/CABG is met at the one-sided 0.025 level of significance

Proprietary confidential information.

© 2016 Boehringer Ingelheim International GmbH or one or more of its affiliated companies. All rights reserved.

This document may not - in full or in part - be passed on, reproduced, published or otherwise used without prior written permission.

Step 4 – Superiority of 110mg DE-DAT to warfarin-TAT in MBE/CRNMBE is met at the one-sided 0.025 level of significance

Step 5 – Non inferiority of 150mg DE-DAT and 110mg DE-DAT combined to warfarin-TAT in DTE is met at the one-sided 0.025 level of significance

Step 6 – Superiority of 150mg DE-DAT to warfarin-TAT in MBE/CRNMBE is met at the one-sided 0.025 level of significance

If any of the steps above fail to meet statistical significance, the testing procedure will stop at that step and subsequent tests will not be performed.

The Non-Inferiority (NI) margin used for MBE/CRNMBE will be 1.38 (on the relative HR scale). See [Section 7.6](#) for a clinical justification of this margin. The upper bound of the Wald confidence interval (CI) of the HR of DE-DAT vs. warfarin-TAT (one-sided 97.5%) will be compared to this NI margin for the NI testing.

